
53. Lin C-W, Zeng X-L, Zhang J-F, et al. Determining the optimal cutoff values of plasma N-terminal Pro- B-type natriuretic peptide levels for the diagnosis of heart failure in children of age up to 14 years. *J Cardiac Fail* 2014;20:168–73.

Appendix 1
Schedule of Assessments
For all Subjects after Confirmation of Final Doses by IMC and SOC

			Abbr. Baseline ¹⁹ (for re-start patients only)	☎ ²²	Home Visit ¹¹	Site	Home Visit ¹¹	☎ ²²	Site	☎ ²²	Home Visit ¹¹	Site	Home Visit ¹¹	☎ ²²	Site	Site	FU (2 W)	FU (6 W)
Week	Screening ² (~4 weeks)	Baseline		2	4	6	8	10	12 ²	14	16	18 ²	20	22	24 ²	EW ²	26	30 ²
Day	-28	1	1	15	29	43	57	71	85	99	113	127	141	155	169	NA	183	211
Time window (days)	-28 to -7	NA	NA	±2	±2	±2	±2	±2	±2	±2	±2	±2	±2	±2	±2	NA	±2	+7
Study site visits	x	x	x			x			x			x			x	x		x
Informed consent	x																	
IQ test ⁸	x																	
ADOS 2 ⁸	x																	
SRS-2	x																	
Inclusion/Exclusion criteria	x																	
Randomization ¹⁷		P																
Demography ⁴	x																	
Medical history (including psychiatry)	x																	
Physical and neurological examination	x		x			x			x			x			x	x		x
Tanner staging ¹²		x 1 week ¹	x 1 week ¹						x						x	x		x
Anthropometric measurements	x	x	x						x						x	x		x

Appendix 1
Schedule of Assessments
For all Subjects after Confirmation of Final Doses by IMC and SOC (cont.)

Week	Screening ² (~4 weeks)	Baseline	Abbr. Baseline ¹⁹ (for restart patients only)	☎ ²²	Home Visit ¹¹	Site	Home Visit ¹¹	☎ ²²	Site	☎ ²²	Home Visit ¹¹	Site	Home Visit ¹¹	☎ ²²	Site	Site	FU (2 W)	FU (6 W)
				2	4	6	8	10	12 ²	14	16	18 ²	20	22	24 ²	EW ²	26	30 ²
Day	-28	1	1	15	29	43	57	71	85	99	113	127	141	155	169	NA	183	211
Time window (days)	-28 to -7	NA	NA	±2	±2	±2	±2	±2	±2	±2	±2	±2	±2	±2	±2	NA	±2	+7
Vital signs	x	P, x ¹⁰	P, x ¹⁰			P, x ¹⁰			P, x ¹⁰			P, x ¹⁰			P, x ¹⁰	x		x
ECG-12 lead	x	P ³	P ¹⁹			x ⁷									x ⁷	x		x
Fasting	x																	
Hematology ²³	x	P	P	(x ²²)	x	(P ²²)	x	(x ²²)	P	(x ²²)	x	(P ²²)	x	(x ²²)	P	x	x	x
Full serum chemistry ⁵	x ⁶	P ⁶	P ⁶						P ⁶						P ⁶	x ⁶		x ⁶
Safety questions ²¹				x	x	x	x	x	x	x	x	x	x	x	x		x	
Coagulation	x															P	x	
Urinalysis	x	P	P			x			x			x			x	x		x
Pregnancy test ¹³	x	P	P						x						x	x		x
Serology	x																	
Substance use ⁹	x								x						x	x		x
Alcohol test ⁹	x								x						x	x		x
Dispensing of study medication		x	x			x			x			x			x ²⁰			
Administration of study medication		x ^P	x ^P	x	x	x	x	x	x	x	x	x	x	x	x			
Palatability									x ¹⁵									

Appendix 1
Schedule of Assessments
For all Subjects after Confirmation of Final Doses by IMC and SOC (cont.)

Week	Screening ² (~4 weeks)	Baseline	Abbr. Baseline ¹⁹ (for restart patients only)	☎ ²²	Home Visit ¹¹	Site	Home Visit ¹¹	☎ ²²	Site	☎ ²²	Home Visit ¹¹	Site	Home Visit ¹¹	☎ ²²	Site	Site	FU (2 W)	FU (6 W)
				2	4	6	8	10	12 ²	14	16	18 ²	20	22	24 ²	EW ²	26	30 ²
Day	-28	1	1	15	29	43	57	71	85	99	113	127	141	155	169	NA	183	211
Time window (days)	-28 to -7	NA	NA	±2	±2	±2	±2	±2	±2	±2	±2	±2	±2	±2	±2	NA	±2	+7
PK blood samples ¹⁴							x		P, x						P, x	x		
Clinical genotyping ¹⁷		x																
Research Biosample Repository (optional)		x																
Vineland™-II (survey)		x 1 week ¹	x 1 week ¹						x						x	x		x
ABC		x 1 week ¹	x 1 week ¹			x			x			x			x	x		x
RBS-R		x 1 week ¹	x 1 week ¹			x			x			x			x	x		x
CaGI									x						x	x		
PedsQL (Family Impact Scale)		x 1 week ¹	x 1 week ¹						x						x	x		
Exit interviews															x	x		
C-SSRS ¹⁸	x	x 1 week ¹	x 1 week ¹			x			x			x			x	x		x
PedsQL (Core and Cognitive Scale)		P 1 week ¹	P 1 week ¹						x						x ¹⁶	x ¹⁶		
OACIS-S		P 1 week ¹	P 1 week ¹			x			x			x			x	x		x

Appendix 1

Schedule of Assessments

For all Subjects after Confirmation of Final Doses by IMC and SOC (cont.)

5. See protocol Section [4.6.1.7](#) and lab manual for more details about full serum chemistry.
6. At screening, Week 24/Early Withdrawal Visit and Follow-Up Visit (6 weeks), glycated hemoglobin (HbA1c), thyroid stimulating hormone (TSH), and free thyroxine (T4) will be assessed. [REDACTED]
7. ECG at Week 6 and Week 24 will be performed 3 hours post-dose.
8. ADOS-2 and IQ test up to 12 months old can be accepted at screening; Wechsler Abbreviated Scale of Intelligence Scale, Second Edition (WASI-II) or Wechsler Preschool and Primary Scale of Intelligence, Fourth Edition (WPPSI-IV) intelligence test will be used at screening.
9. Alcohol test and substance use tests are mandatory at screening for adolescents. At other visits and for children, only to be performed if deemed necessary by investigator.
10. Vital signs will be done pre-dose and 3 hours post-dose. Additionally, orthostatic function will be assessed pre-dose and 3 hours post-dose at baseline/abbreviated baseline, and 3 hours post-dose at Week 6 and Week 24 or Early Withdrawal Visit.
11. Planned as off-site/home visit and can be done by a nurse, however can also be performed as clinic visits.
12. Tanner staging will be done in patients 7 years and older, but not after menarche in female patients and not after voice break in male patients.
13. Pregnancy tests will be performed in female patients after menarche only.
14. PK samples: Week 8: in the evening post-dose together with safety labs; Week 12 and Week 24: pre + 2 hours post-dose + end of visit but at least 4 hours post-dose; Early Withdrawal Visit: one at any time. Samples scheduled at least 4 hours post-dose on a clinic visit day can be taken by a nurse at home.
15. Subject and caregiver will provide feedback on palatability of study medication.
16. Subjects will be asked additional questions after completion of the PedsQL.
17. RBR and CG samples should be taken at baseline upon consent, but if missed, may be taken at any visit after.
18. For children 5–11 years old, additional questions will be asked in context of Columbia-Suicide Severity Rating Scale (C-SSRS; see Section [4.6.1.12](#)).
19. Subjects from first adolescent/first children cohorts who stopped treatment on or before Week 8 in the context of the IMC/SOC dosing decision (see [Appendix 2](#), Section [3.1.3.1](#)) will be allowed to restart for an additional 24 weeks in the main study in the same treatment arm without new randomization, provided the investigator can exclude relevant changes in patient's general condition (see Section [4.2.1](#)). These patients will have a new, abbreviated baseline visit, and will continue with all subsequent visits according to the schedule of assessments. In this abbreviated baseline visit, a single ECG should be taken.
20. For those subjects who consent to the OLE and are able to proceed directly into the OLE, medication will be administered after all assessments are complete. This will be defined as Day 1 of the OLE.

Appendix 1
Schedule of Assessments
For all Subjects after Confirmation of Final Doses by IMC and SOC (cont.)

21. Safety monitoring will follow semi-structured interview as listed in [Appendix 8](#). This will include a check on compliance with body temperature monitoring.
22. If these hematology samples are required, visits must be conducted either at the site or by a home nurse if appropriate.
23. *Blood samples indicated in parentheses are applicable only in the event that temperature monitoring could be implemented or individuals are not compliant.*

Appendix 2
Schedule of Assessments
For First Cohorts of 24 Adolescents and 30 Children
until Confirmation of Final Doses by IMC/SOC

	Screening ² (~4 weeks)	Baseline	Home Visit at W1	W2	W4 ²	W6 ²	Home Visit ¹¹ at W8	For Discontinuation and Stopping Treatment Only ¹⁶		
								EoT ²	FU (2 W)	FU (6 W) ²
Day	-28	1	8	15	29	43	57		14	42
Time window (days)	-28 to -7	NA	±2	±2	±2	±2	±2	NA	±2	+7
Study site visits	x	x		x	x	x	For details about Week 8 visit see Appendix 1 and continue according to Appendix 1.	x		x
Informed consent	x									
IQ test ⁸	x									
ADOS 2 ⁸	x									
SRS-2	x									
Inclusion/Exclusion criteria	x									
Randomization ¹⁷		P								
Demography ⁴	x									
Medical history (incl. psychiatry)	x									
Physical and neurological examination	x					x			x	x
Tanner staging ¹²		x 1 week ¹								

Appendix 2
Schedule of Assessments
For First Cohorts of 24 Adolescents and 30 Children
until Confirmation of Final Doses by IMC/SOC (cont.)

[figure not shown]
	Screening ² (~4 weeks)	Baseline	Home Visit at W1	W2	W4 ²	W6 ²	Home Visit ¹¹ at W8	For Discontinuation and Stopping Treatment Only ¹⁶		
								EoT ²	FU (2 W)	FU (6 W) ²
Day	-28	1	8	15	29	43	57		14	42
Time window (days)	-28 to -7	NA	±2	±2	±2	±2	±2	NA	±2	+7
Anthropometric measurements	x	x					For details about week 8 visit see Appendix 1 and continue according to Appendix 1			x
Vital signs	x	P, x ¹⁰		P, x ¹⁰	P	P, x ¹⁰		x		x
ECG-12 lead	x	P ³		x ⁷	P	x ⁷		x		x
Fasting	x									
Hematology	x	P		P	P	P		x	x	x
Full serum chemistry ⁵	x ⁶	P ⁶			P			x ⁶		x ⁶
Coagulation	x									
Urinalysis	x	P				x		x		x
Pregnancy test ¹³	x	P								x
Serology	x									
Substance use ⁹	x									x
Alcohol test ⁹	x									x
Dispensing of study medication		x				x				
Administration of study medication		x ^P	x	x	x	x				
PK blood samples ¹⁴			P	P, x	P			x		
Clinical genotyping ¹⁷		x								

[figure not shown]
Appendix 2
Schedule of Assessments
For First Cohorts of 24 Adolescents and 30 Children
until Confirmation of Final Doses by IMC/SOC (cont.)

[figure not shown]
	Screening ² (~4 weeks)	Baseline	Home Visit at W1	W2	W4 ²	W6 ²	Home Visit ¹¹ at W8	For Discontinuation and Stopping Treatment Only ¹⁶		
								EoT ²	FU (2 W)	FU (6 W) ²
Day	-28	1	8	15	29	43	57		14	42
Time window (days)	-28 to -7	NA	±2	±2	±2	±2	±2	NA	±2	+7
Research Biosample Repository (optional)		x					For details about week 8 visit see Appendix 1 and continue according to Appendix 1			
Vineland™-II (survey)		x 1 week ¹								
ABC		x 1 week ¹				x		x		x
RBS-R		x 1 week ¹				x		x		x
PedsQL (Family Impact Scale)		x 1 week ¹								
C-SSRS ¹⁸	x	x 1 week ¹		x	x	x		x		x
PedsQL (Core and Cognitive Scale)		P 1 week ¹								
OACIS-S		P 1 week ¹				x		x		x
OACIS-I						x		x		x

[figure not shown]
Appendix 2 Schedule of Assessments For First Cohorts of 24 Adolescents and 30 Children until Confirmation of Final Doses by IMC/SOC (cont.)

[figure not shown]
3. Triplicate ECG at baseline only.
4. Demography includes Educational Level, Diagnosis of ASD, Caregiver Information, Employment and/or school Status and Living Arrangements.
5. See protocol Section 4.6.1.7 and lab manual for more details about full and abbreviated serum chemistry.
6. At screening and Follow-Up Visit (6 weeks) glycated hemoglobin (HbA1c), thyroid stimulating hormone (TSH), and free thyroxine (T4) will be assessed. [REDACTED]
7. At Week 2 and Week 6, a single ECG 3 hours post-dose; at Week 4 a single ECG preferably pre-dose.
8. ADOS-2 and IQ test up to 12 months old can be accepted at screening; Wechsler Abbreviated Scale of Intelligence Scale, Second Edition (WASI-II) or Wechsler Preschool and Primary Scale of Intelligence, Fourth Edition (WPPSI-IV) intelligence test will be used at screening.
9. Alcohol test and substance use tests are mandatory at screening for adolescents. At other visits and for children only to be performed if deemed necessary by investigator.
10. Vital signs will be done pre-dose and additionally 3 hours post-dose at baseline, Week 2 and Week 6. Orthostatic function will be assessed 3 hours post-dose at baseline and Week 6.
11. Planned as off-site/home visit and can be done by a nurse, however can also be performed as clinic visits.
12. Tanner staging will be done in patients 7 years and older, but not after menarche in female patients and not after voice break in male patients.
13. Pregnancy tests will be performed in female patients after menarche only.
14. PK samples: Week 1: pre-dose; Week 2: pre; + 2 (+/- 0.5); hour + 4 (+/- 0.5) hour + at least 6 hours post-dose; PK samples need to be at least 2 hours apart; Week 4: pre-dose; End of Treatment Visit: one at any time. Samples scheduled at least 4 hours post-dose on a clinic visit day can be taken by a nurse at home.
15. If treatment continues without halt and with final doses determined, ongoing patients will have their next visit (e.g., visit Week 8) according to [Appendix 1](#) and continue from thereafter according to [Appendix 1](#).
16. *Subjects can continue in the study beyond 8 weeks, even if dose confirmation has not occurred, as long as individual review of PK has been completed and exposure is within agreed limits.*
17. RBR and clinical genotyping (CG) samples should be taken at baseline upon consent, but if missed, may be taken at any visit after.
18. For children 5–11 years old additional questions will be asked in context of Columbia-Suicide Severity Rating Scale (C-SSRS; see Section 4.6.1.12).

[figure not shown]

Appendix 6 Tanner Stages [48]

Stage	Male Genitalia	Pubic Hair	Female Breasts
1	Preadolescent testes, scrotum, and penis are childlike in size	None; may be vellus hair, as over abdomen	Preadolescent elevation of papilla only
2	Slight enlargement of scrotum with reddening of skin; little or no enlargement of penis	Sparse growth of long, slightly pigmented, downy hair, straight or slightly curled, primarily at base of penis or along labia	Breast bud stage; breast and papilla form a small mound; areolar diameter enlarges
3	Further enlargement of scrotum; penis enlarges, mainly in length	Hair considerably darker, coarser, and more curled; spreads sparsely over junction of pubes	Further enlargement of breast and areola with no separation of their contours
4	Further enlargement and darkening of scrotum; penis enlarges, especially in breadth; glans develops	Adult-type hair that does not extend onto thighs, covering a smaller area than in adult	Areola and papilla project to form a secondary mound above the contour of the breast; stage 4 development of the areolar mound does not occur in 10% of girls and is slight in 20%; when present, it may persist well into adulthood
5	Adult in size and shape	Adult in quantity and type with extension onto thighs but not up linea alba	Mature female; papilla projects and areola recesses to general contour of breast

In boys, if different scores are obtained for pubic hair and genitalia, the score for genitalia should be used.

In girls, if different scores are obtained for pubic hair and breast development, the score for breast development should be used.

In this study Tanner staging will be done in subjects 7 years and older, but not after menarche in female and not after voice break in male subjects

Appendix 7

[figure not shown]
Strong and Moderate Inhibitors and Inducers of CYP3A [37]

[figure not shown]
Concomitant administration of strong Cytochrome P450 3A4 (CYP3A) inducers or inhibitors is prohibited. Moderate CYP3A inhibitors are also prohibited, but for treatment duration of shorter than approximately 10 days (e.g., in the context of an adverse event) possible exceptions can be discussed with the Sponsor (Medical Monitor or designee).

Based on in vitro experiments, quinidine should not be given with balovaptan, but no systemic interactions are predicted with cetirizine, dabigatran etexilate, or digoxin. Caution is advised when using balovaptan together with other medications known to be clinically-relevant substrates of P-gp, in particular for those medications that have a narrow therapeutic window (e.g., loperamide). However, when such medications are dosed 5 or more hours after administration of balovaptan, the risk of pharmacokinetic interaction is predicted to be small.

CYP3A Inhibitor*	CYP3A Inducer*
Itraconazole	St John's wort
Clarithromycin	Dexamethasone
Ketoconazole	Retinoic acid
Grapefruit juice	Carbamazepine
Erythromycin	Phenytoin
Diltiazem	Rifampin
Verapamil	
Ciprofloxacin	
Clotrimazole	
Fluconazole	
Tofisopam	

* This table is not exhaustive.

Appendix 9 Schedule of Assessments: Open-Label Extension for Weeks 24 to 52

	Unique to substudy (see Appendix 11)		☎ ¹⁹	Home Visit ¹¹	Site	Home Visit ¹¹	☎ ¹⁹	Site	☎ ¹⁹	Home Visit ¹¹	Site	Home Visit ¹¹	☎ ¹⁹	Home Visit ¹¹	☎ ¹⁹	Site
	Week	Day	26	28	30 ²	32	34	36 ²	38	40	42 ²	44	46	48	50	52 ²
Time window (days)	-14 to -1	1	183	197	211	225	239	253	267	281	295	309	323,	337	351	365
	± 7	± 2	± 2	± 2	± 2	± 2	± 2	± 2	± 2	± 2	± 2	± 2	± 2	± 2	± 2	± 2
Informed consent	x															
Medical history	x															
Demography ⁴	x															
Physical and neurological examination	x				x			x			x					x
Tanner staging ¹²	x							-								x
Anthropometric measurements	x							x								x
Vital signs	x				P, x ₁₀			P, x			P, x					P, x
ECG-12 lead	x ³				x ⁷											x ⁷
Hematology	x		(x ¹⁷)	x	(P)	x	(x ¹⁷)	P	(x ¹⁷)	x	(P)	x	(x ¹⁷)	x	(x ¹⁷)	P
Full serum chemistry ⁵	x ⁶							P								P ⁶
Safety questions ¹⁶			x	x	x	x	x	x	x	x	x	x	x	x	x	x
Coagulation	x															P
Urinalysis	x				x			x			x					x
Pregnancy test ⁹	x				x			x			x					x

Appendix 9

Schedule of Assessments: Open-Label Extension to Week 52 (cont.)

Week	Unique to substudy (see Appendix 11)		☎ ¹⁹	Home Visit ¹¹	Site	Home Visit ¹¹	☎ ¹⁹	Site	☎ ¹⁹	Home Visit ¹¹	Site	Home Visit ¹¹	☎ ¹⁹	Home Visit ¹¹	☎ ¹⁹	Site
			26	28	30 ²	32	34	36 ²	38	40	42 ²	44	46	48	50	52 ²
Day	-14 to -1	1	183	197	211	225	239	253	267	281	295	309	323,	337	351	365
Time window (days)	± 7	± 2	± 2	± 2	± 2	± 2	± 2	± 2	± 2	± 2	± 2	± 2	± 2	± 2	± 2	± 2
Alcohol / Substance use ⁸	x															x
Dispensing of study medication		x			x			x			x					x
Administration of study medication		x	x	x	x	x	x	x	x	x	x	x	x	x	x	x
PK blood samples ¹³								P								x
Vineland™-II (survey)		x ¹						x								x
ABC		x ¹						x								x
RBS-R		x ¹						x								x
CaGI								x								x
PedsQL (Family Impact Scale) ¹⁵		x ¹						x								x
C-SSRS ¹⁴		x			x			x			x					x
PedsQL (Core and Cognitive Scale)		x ¹						x								x
CGI-S		x			x			x			x					x
CGI-I					x			x			x					x
Body temperature monitoring								← Temperature monitoring every 2 weeks →								
Adverse events	SAE only															
Previous and concomitant treatments	x	x														

Appendix 9

Schedule of Assessments: Open-Label Extension to Week 52 (cont.)

ABC=Aberrant Behavior Checklist; CaGI=Caregiver-reported Global Impression; CGI-I=Clinical Global Impressions of Improvement; CGI-S=Clinical Global Impressions of Severity; CPK=creatinine phosphokinase; ECG=electrocardiogram; EW=Early Withdrawal; FU=Follow-Up; ██████████/██████████ T; PedsQL=Pediatric Quality of Life; PK=pharmacokinetic; RBS-R=Repetitive Behavior Scale-Revised; SAE=serious adverse event; W=Week(s).

- ☎ Phone call interview
- P Pre-dose. The first dose of study medication has to be taken after all pre-dose assessments.
- 1 These assessments can be performed at or within 1 week prior to first dose.
- 2 If necessary, these clinic visits (Week 30, Week 36, Week 42, Week 52, Early Withdrawal Visit, and 6-week Follow-Up Visit) can be performed over 2 consecutive days; assessments at screening can be performed over the entire screening time window. After premature discontinuation, an Early Withdrawal Visit should be arranged as soon as possible (see also Section 4.7.1.1).
- 3 Triplicate ECG at rescreening (substudy) only.
- 4 Demography includes Educational Level, Diagnosis of ASD, Caregiver Information, Employment and/or school Status, and Living Arrangements
- 5 See Section 4.6.1.7 and lab manual for more details about full serum chemistry ██████████.
- 6 At rescreening (substudy only), Week 76/Early Withdrawal Visit and Follow-Up Visit (6 weeks), glycated hemoglobin (HbA1c), thyroid stimulating hormone (TSH), and free thyroxine (T4) will be assessed. ██████████
- 7 ECG at Week 30 will be performed 3 hours post-dose.
- 8 Alcohol test and substance use tests are mandatory at screening for adolescents. At other visits and for children, only to be performed if deemed necessary by investigator.
- 9 Pregnancy tests will be performed in female patients after menarche only.
- 10 Vital signs will be done pre-dose and 3 hours post--dose. Additionally, orthostatic function will be assessed pre-dose and 3 hours post-dose at Week 30.
- 11 Planned as off-site/home visit and can be done by a nurse, however can also be performed as clinic visits.
- 12 Tanner staging will be done in patients 7 years and older, but not after menarche in female patients and not after voice break in male patients.
- 13 PK samples should be collected in those that withdraw from the study early as long as ≤7 days after last dose.
- 14 For children 5–11 years old, additional questions will be asked in context of Columbia-Suicide Severity Rating Scale (C-SSRS; see Section 4.6.1.12).
- 15 Patients will be asked additional questions after completion of the PedsQL.
- 16 Safety interview will occur either at site or during telephone visit and will follow semi-structured interview as listed in Appendix 8. It will include a check on compliance with body temperature monitoring.
- 17 If these hematology samples are required, visits must be conducted either at the site or by a home nurse if appropriate.

Appendix 10
Schedule of Assessments: Open-Label Extension from Weeks 52 to 76

	Site	Site	Site	FU (2 W)	FU (6 W)
Week	64 ²	76 ²	EW ²	78	88 ²
Day	449	533	NA		
Time window (days)	±2	±2	NA	±2	7
Study site visits	x	x	x		x
Informed consent					
Physical and neurological examination	x	x	x		x
Tanner staging ³					x
Anthropometric measurements	x	x	x		x
Vital signs		x	x		x
ECG-12 lead		x	x		x
Hematology	P	x	x	x	x
Full serum chemistry ⁵	P	x ⁶	x ⁶		x ⁶
Safety questions ¹	x	x	x	x	
Coagulation		x	x		
Urinalysis		x	x		x
Pregnancy test ⁴	x	x	x		x
Dispensing of study medication	x				
Administration of study medication	x	x	x		
PK blood samples		x	x ⁷		

Appendix 10

Schedule of Assessments: Open-Label Extension to Week 76 (cont.)

- 2 If necessary these clinic visits (Week 64, Week 76, Early Withdrawal Visit, and 6-week Follow-Up Visit) can be performed over 2 consecutive days; assessments at screening can be performed over the entire screening time window. After premature discontinuation, an Early Withdrawal Visit should be arranged as soon as possible (see also Section [4.7.1.1](#))
- 3 Tanner staging will be done in patients 7 years and older, but not after menarche in female patients and not after voice break in male patients.
- 4 Pregnancy tests will be performed in female patients after menarche only.
- 5 See Section [4.6.1.7](#) and lab manual for more details about full serum chemistry.
- 6 At rescreening (substudy only), Week 76/Early Withdrawal Visit, and Follow-Up Visit (6 weeks), glycated hemoglobin (HbA1c), thyroid stimulating hormone (TSH), and free thyroxine (T4) will be assessed.
- 7 PK samples should be collected in those that withdraw from the study early.
- 8 For children 5–11 years old, additional questions will be asked in context of Columbia-Suicide Severity Rating Scale (C-SSRS; see Section [4.6.1.12](#)).
- 9 Patients will be asked additional questions after completion of the PedsQL.

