3.1.1 Overview of Study Design

The total duration of the study (from screening through to study completion) for each subject will be approximately 87 weeks divided as follows:

[figure not shown]
- Screening period (first adolescent/children cohorts): Approximately 4 weeks
 - at least 1 week and up to 4 weeks prior to randomization
- Screening period (main study): Approximately 4 weeks
 - at least 1 week and up to 4 weeks prior to randomization
- Treatment phase*: 24 weeks
- Optional OLE: Approximately 52 weeks
- Follow-up: At least 6 weeks and up to 7 weeks after last dose

* A small group of subjects may receive blinded treatment for up to 32 weeks. These are subjects from the first PK cohort who stopped treatment prior to determination of final doses by the IMC and SOC, and have the opportunity to re-start in the main study (see protocol Section 3.1.3.1).

Approximately 340 children and adolescents aged 5–17 years with ASD will be recruited to ensure a total of 160 evaluable subjects *with placebo or 10 mg eq after 24 weeks of treatment (see Figure 1 and Figure 2)*. All individuals who received doses of balovaptan that were not equivalent to 4 mg or 10 mg will not be included in the primary analysis.

[figure not shown]
Randomization will be stratified by age group and sex. The ratio between adolescents (aged 13–17 years) and children (aged 5–12 years) will be approximately 1:1. The children’s cohort should contain up to approximately 30 subjects of whom up to approximately 16 should be aged between 5 and 7 years old. Additionally, the proportion of female subjects will be balanced in each treatment group and limited to a maximum of 20% of the entire study population.

Figure 1 Study Design for Subjects Enrolled prior to Version 6

Subjects will be randomized in a ratio of 1:1:1 and receive doses providing an exposure approximately equivalent to the 4 mg/day and 10 mg/day or placebo exposures observed in adults (see [Table 1](#) for predicted doses). Age-adjusted doses were derived using a physiologically-based pharmacokinetic (PBPK) model.

Figure 2 Study Design for Subjects Enrolled in Accordance to Version 6

eq = equivalent.

Subjects will be randomized in a ratio of 1:1 and receive doses equivalent to the 10 mg/day or placebo exposures observed in adults (see [Table 2](#) for predicted doses).

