4.6.2.2 Assessments during Treatment

All assessments must be performed as per Schedule of assessments (see Appendix 1, Appendix 2, Appendix 9, and Appendix 10).

Subjects will arrive at each study visit without having taken their daily dose of study medication. Following collection of the pre-dose PK blood sample, and the safety labs

subjects will take their next dose of study medication. Site staff will record the actual date and time of the dose intake. The last dose of study medication will be administered at the Week 76 visit.

When blood samples are scheduled for the same nominal time as other assessments the following order should be followed:

- 12-lead ECGs
- Vital signs
- Blood samples

As a general rule, the test sequence for all disease specific assessments should remain the same for a given subject as established at screening and Baseline. Additionally, testing should occur around the same time of the day at each visit.

For the informant based assessments the following order will be followed:

- Always the Vineland™-II will be the first informant based assessment with the caregiver.
- For all other informant based assessments there is no restriction in the order, however a sequence established at screening and Baseline should remain the same for a given subject.

The patient reported outcome measures can be performed in parallel with the informant based assessments. The following sequence is proposed: first the C-SSRS followed by the PedsQL. Ideally these assessments should be performed before administration of study medication or within 1 hour after administration.

The remaining clinician-completed measures will be completed after all other disease specific assessment to minimize any possible bias on caregiver reported assessments.

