4.6.2.4 Follow-Up Assessments

As per the schedule of assessments, all subjects will have safety hematology/CPK blood samples taken 2 weeks after last dose and a clinic visit 6 weeks after last dose (see [Appendix 1](#) or [Appendix 10](#)). After the study completion/Early Withdrawal visit, adverse events should be followed as outlined in Sections [5.5](#) and [5.6](#).

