5.3.1 Adverse Event Reporting Period

Investigators will seek information on adverse events at each subject contact. All adverse events, whether reported by the subject or noted by study personnel, will be recorded in the subject's medical record. Adverse events will then be reported on the Adverse Event eCRF as follows:

After informed consent has been obtained **but prior to initiation of study drug**, only serious adverse events caused by a protocol-mandated intervention should be reported (e.g., serious adverse events related to invasive procedures such as biopsies). Any other adverse event should not be reported.

After initiation of study drug, all adverse events, regardless of relationship to study drug, will be reported until 6 weeks after the last dose of study drug.

After a period of 6 weeks from the last dose of study drug, Investigators should only report any deaths, serious adverse events, or other adverse events of concern that are believed to be related to prior treatment with study drug (see Section [5.6](#)).

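### Appendix 10 dates the 6-week follow-up visit of the open-label extension at Week 88; six weeks after the Week 76 last dose is Week 82

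*Protocol*

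**What the plan says.** Protocol Appendix 10 covers the open-label extension (OLE) from Week 52 to Week 76 and the follow-up after it. Its week row reads "Week 64 ² 76 ² EW ² 78 88 ²". The last two columns are headed as the 2-week and 6-week follow-ups. Week 76 is given as Day 533. The day cells under both follow-up columns are blank in the supplied text, and the window for the last column is 7 days.

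The other statements on timing are:

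- Section 4.6.2.2: "The last dose of study medication will be administered at the Week 76 visit".
- Section 4.6.2.4, which cites Appendices 1 and 10: "all subjects will have safety hematology/CPK blood samples taken 2 weeks after last dose and a clinic visit 6 weeks after last dose".
- Section 3.1.1: "Follow-up: At least 6 weeks and up to 7 weeks after last dose".
- Appendix 10, footnote 2: "If necessary these clinic visits (Week 64, Week 76, Early Withdrawal Visit, and 6-week Follow-Up Visit) can be performed over 2 consecutive days".
- Appendix 10, footnote 6, names the visit again when it lists the extra thyroid and HbA1c tests: "At rescreening (substudy only), Week 76/Early Withdrawal Visit, and Follow-Up Visit (6 weeks), glycated hemoglobin (HbA1c".
- Section 5.3.1, on adverse events after study drug has started: they "will be reported until 6 weeks after the last dose of study drug".
- Section 3.2 expects the last observation about 83 weeks after the last enrolment, and Section 3.1.1 gives about 87 weeks in total per subject.

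**The concern.** The column heading and the week number in Appendix 10 contradict each other. Counted from the Week 76 dose, the neighbouring Week 78 is two weeks later, as its heading says, but Week 88 is twelve weeks later under a heading of six.

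Sites book visits from this table. Section 4.2.4 has subjects who enter the OLE complete their treatment follow-up visit at the end of the OLE. For a subject who goes straight from the blinded phase through to Week 76, this column is therefore the only scheduled clinic visit off drug; the 2-week column carries no site-visit mark. The 6-week column holds the physical and neurological examination, vital signs, ECG, hematology, full chemistry, urinalysis and pregnancy test, and it is the only column in Appendix 10 marked for Tanner staging. Followed literally, Week 88 would delay all of these in children and adolescents until after the routine adverse event reporting period in Section 5.3.1 has ended.

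**Working it through.** **Rule.** Study day = 7 × week + 1, and follow-up week = last-dose week + offset.

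**Does the rule reproduce the protocol's own entries?**

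- Appendix 10: Week 64 gives 7 × 64 + 1 = 449, and Week 76 gives 7 × 76 + 1 = 533. Both are as printed.
- Appendix 1, double-blind phase: the end of its day row is "141 155 169 NA 183 211". Week 24 gives 169. The 2-week follow-up gives 169 + 14 = 183, which is Week 26. The 6-week follow-up gives 169 + 42 = 211, which is Week 30. All are as printed.

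**Applied to Appendix 10 (last dose Week 76, Day 533)**

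| Visit | Expected week | Expected day | Printed week |
|---|---|---|---|
| 2-week follow-up | 76 + 2 = 78 | 533 + 14 = 547 | 78 |
| 6-week follow-up | 76 + 6 = 82 | 533 + 42 = 575 | 88 |
| 6-week follow-up, end of 7-day window | 76 + 7 = 83 | 533 + 49 = 582 | not applicable |

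**Size of the discrepancy.** Week 88 is Day 7 × 88 + 1 = 617.

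- Time from last dose: 617 − 533 = 84 days, against 42 to 49 intended.
- Past the end of the visit window: 617 − 582 = 35 days.
- Past the end of routine adverse event reporting (six weeks after last dose, Day 575): 617 − 575 = 42 days.

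**Can another reading give 88?** The upper end of the follow-up range gives 76 + 7 = 83. Counting six weeks from the 2-week follow-up gives 78 + 6 = 84. Neither reaches 88.

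**Cross-check against the stated durations**

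- Enrolment to last observation (Section 3.2, about 83 weeks): 24 + 52 + 7 = 83.
- Total per subject (Section 3.1.1, about 87 weeks): 4 + 24 + 52 + 7 = 87.
- With a Week 88 visit these become 88 and 4 + 88 = 92 weeks, or 89 and 93 with the 7-day window.

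The stated durations therefore fit a final visit at Week 82 to 83 and do not fit Week 88.

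**The case against.** The strongest objection concerns the source. The point rests on one digit in a table that was visibly damaged when the PDF was read. The follow-up day cells are blank. The window is an unsigned 7 where Appendix 1 has +7. Footnote 1 is called but not listed, and footnotes 8 and 9 explain assessments whose rows are not in the supplied table. A misread character would look the same as an author's slip. This stands as a limit on confidence, and a look at the source PDF settles it. Against it, the other week and day numbers in the table read cleanly and obey the arithmetic.

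Second, the document largely corrects itself. The heading sits directly above the number, two footnotes and Sections 3.1.1 and 4.6.2.4 say six weeks (or six to seven), and many sites would follow the words. That is true, and it is why the point is minor. It does not make the number right, and no day entry in the supplied text corrects it.

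Third, the consequences are limited:

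- The reporting period in Section 5.3.1 runs from the last dose whatever the visit date, and a late visit could still elicit events that began within it.
- After six weeks, deaths, serious events and other events of concern believed related to study drug remain reportable.
- Week 78 still has hematology and the safety questions.
- Early withdrawals are timed from their own last dose, so only subjects who complete Week 76 are affected.
- Section 3.2 defines the end of study by the last observation itself, so a later visit would move that date and not fall outside the study.

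All of this is correct. What remains is a delay of about six weeks in laboratory, ECG and examination checks, not a loss of adverse event reporting.

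Finally, absolute study days are not the protocol's only convention: Appendix 2 gives its follow-up columns as Day 14 and Day 42. The day entries are therefore useful but secondary to the week number.

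**Conclusion.** The inconsistency is real. The 6-week follow-up after the OLE belongs at Week 82 (Day 575), or up to Week 83 (Day 582) with the window. The printed Week 88 is six weeks too late. Every worded statement and both stated durations agree on this, so it is most likely a slip in one cell.

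Severity is minor. The effect is operational, confined to safety follow-up of subjects who complete the OLE, and arises only if a site follows the number against its heading. The primary and planned inferential analyses are untouched. Confidence is medium. The conclusion assumes that the digit was read correctly from the PDF and that the last dose is taken at Week 76 as Section 4.6.2.2 states.

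**What to change.** After checking the source table, change the 6-week follow-up column in Appendix 10 from Week 88 to Week 82, Day 575, with the window written as +7 days to match Appendix 1. If the day cell for the 2-week follow-up is also blank in the source, enter Day 547 (±2).

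The cost is one week number and up to two day entries in one table. No visits or samples are added, and the SAP does not change.
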